7.2.4. Physician's Global Vitiligo Assessment (Total Body)

The severity of total body vitiligo will be assessed by the physician using the PhGVA, which has a 5-point scale ([Table 4](#)). Response will be reported for total body (T-PhGVA).

Table 4: Total Body Physician's Global Vitiligo Assessment Scale

Score	Severity	Description
0	Clear	No signs of vitiligo or complete/near complete repigmentation
1	Almost Clear	Mostly pigmented areas with small depigmented or difficult to repigment areas (eg, hands, feet, philtrum, nares, corners of eyes, perioral skin)
2	Mild Disease	Modest areas of depigmentation with approximately 50% pigmentation within vitiligo areas or significant perifollicular pattern present
3	Moderate Disease	Large areas of depigmented vitiligo areas; significant depigmentation within vitiligo areas
4	Severe Disease	Extensive areas of vitiligo with complete depigmentation

An T-PhGVA of clear (0) or almost clear (1) can be interpreted as T-PhGVA response.

7.2.5. Patient-Reported Outcomes

Patient-reported outcomes and quality of life will be assessed using the following tools:

- VNS (Section [7.2.5.1](#))
- Color-matching question (Section [7.2.5.2](#))
- F-PaGIC-V (Section [7.2.5.3](#))
- T-PaGIC-V (Section [7.2.5.4](#))
- DLQI or CDLQI (Section [7.2.5.5](#))
- WHO-5 (Section [7.2.5.6](#))
- TSQM (Section [7.2.5.7](#))

- VitiQoL (Section [7.2.5.8](#))
- HADS (Section [7.2.5.9](#))

7.2.5.1. Vitiligo Noticeability Scale

The VNS is a patient-reported measure of vitiligo treatment success, which has a 5-point scale ([Batchelor et al 2016](#)). The baseline facial photograph will be shown to the participants for reference, and a mirror will be provided for the participants to assess the vitiligo on their face. The participant will be asked to respond to the following query:

Compared with before treatment, how noticeable is the vitiligo now? Responses: (1) More noticeable, (2) As noticeable, (3) Slightly less noticeable, (4) A lot less noticeable, and (5) No longer noticeable.

VNS scores of 4 or 5 can be interpreted as representing treatment success.

7.2.5.2. Color-Matching Question

The baseline photograph and current participants' facial image (participants will be provided a mirror) will be shown to the participant for reference, and the participant will be asked to respond to the following query:

At this point of your treatment, how well does your skin color match between your face treated vitiligo skin and face normal skin? Responses: (1) Excellent, (2) Very good, (3) Good, (4) Poor, and (5) Very poor.

7.2.5.3. Patient Global Impression of Change-Vitiligo (Facial)

The F-PaGIC-V is an assessment of improvement by the participant. It is a 7-point scale comparing the vitiligo areas at baseline with the participant's treated areas of facial vitiligo at the study visit. Response will be reported for face (F-PaGIC-V). The baseline photograph and current participants' facial image (participants will be provided a mirror) will be shown to the participant for reference. The participant will be asked to respond to the following query:

Since the start of the treatment you've received in this study, your vitiligo on your face treated with the study drug is: (1) Very much improved, (2) Much improved, (3) Minimally improved, (4) No change, (5) Minimally worse, (6) Much worse, and (7) Very much worse.

F-PaGIC-V scores of 1 or 2 can be interpreted as representing treatment success.

7.2.5.4. Patient Global Impression of Change-Vitiligo (Total Body)

The T-PaGIC-V is an assessment of improvement by the participant. It is a 7-point scale comparing the vitiligo areas at baseline with the participant's treated areas of total body vitiligo at the study visit. Response will be reported for total body (T-PaGIC-V). The participant will be asked to respond to the following query:

Since the start of the treatment you've received in this study, your vitiligo on your total body treated with the study drug is: (1) Very much improved, (2) Much improved, (3) Minimally improved, (4) No change, (5) Minimally worse, (6) Much worse, and (7) Very much worse.

T-PaGIC-V scores of 1 or 2 can be interpreted as representing treatment success.

7.2.5.5. Dermatology Life Quality Index

The DLQI ([Finlay and Khan 1994](#)) is a simple 10-question validated questionnaire for use in participants aged 16 years and over to measure how much the skin problem has affected the participant over the previous 7 days.

The scoring of each question is as follows: Very much = 3; A lot = 2; A little = 1; Not at all = 0; Not relevant = 0; Question 7, “Prevented work or studying” = 3.

The following imputation will be applied for incorrectly completed questionnaires:

- If 1 question is left unanswered, this is scored 0 and the scores are summed and expressed as usual out of a maximum of 30.
- If 2 or more questions are left unanswered, the questionnaire is not scored.
- If Question 7 is answered “yes,” this is scored 3. If Question 7 is answered “no,” but then either “a lot” or “a little” is ticked, this is then scored 2 or 1. If “Not relevant” is ticked, the score for Question 7 is 0. If it is answered “no,” but the second half is left incomplete, the score will remain 0.
- If 2 or more response options are ticked, the response option with the highest score should be recorded.
- If there is a response between 2 tick boxes, the lower of the 2 score options should be recorded.
- For DLQI 6 subscales, if the answer to 1 question in a subscale is missing, that subscale should not be scored.

The DLQI is calculated by summing the score of each question resulting in a maximum of 30 and a minimum of 0. The higher the score, the more quality of life is impaired.

The meaning of total DLQI scores can be categorized as follows:

- 0 to 1 = No effect
- 2 to 5 = Small effect
- 6 to 10 = Moderate effect
- 11 to 20 = Very large effect
- 21 to 30 = Extremely large effect

A change from baseline in DLQI and CDLQI score of at least 4 points is considered clinically important ([Basra et al 2015](#), [Waters et al 2010](#)).

The questionnaire is also analyzed under 6 subscales as follows:

- Symptoms and feelings (Questions 1 and 2)
- Daily activities (Questions 3 and 4)
- Leisure (Questions 5 and 6)
- Work and school (Question 7)

- Personal relations (Questions 8 and 9)
- Treatment (Question 10)

CDLQI ([Lewis-Jones and Finlay 1995](#)) is the youth/children's version of the DLQI and will be completed by adolescents aged ≥ 12 years to < 16 years. The scoring of each question is Very much = 3; Quite a lot = 2; Only a little = 1; Not at all = 0; Question unanswered = 0; Question 7: "Prevented school" = 3. The CDLQI is calculated by summing the score of each question resulting in a maximum of 30 and a minimum of 0. The higher the score, the more quality of life is impaired.

The questionnaire is also analyzed under 6 subscales as follows:

- Symptoms and feelings (Questions 1 and 2)
- Leisure (Questions 4, 5, and 6)
- School or holidays (Question 7)
- Personal relationships (Questions 3 and 8)
- Sleep (Question 9)
- Treatment (Question 10)

The severity banding for CDLQI scores is as follows:

- 0 to 1 = No effect on child's life
- 2 to 6 = Small effect
- 7 to 12 = Moderate effect
- 13 to 18 = Very large effect
- 19 to 30 = Extremely large effect

The following imputation will be applied for incorrectly completed questionnaires for CDLQI:

1. If 1 question is left unanswered, this is scored 0, and the scores are summed and expressed as usual out of a maximum of 30.
2. If 2 or more questions are left unanswered, the questionnaire is not scored.
3. If both parts of Question 7 are completed, the higher of the 2 scores should be counted.

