7.5.1.1. Continuous Efficacy Endpoints

By-visit summary statistics for the following continuous measurements, including actual measurement, change from baseline, and percentage change from baseline, will be presented:

- F-VASI/T-VASI
- F-BSA/T-BSA
- DLQI (or CDLQI) Total score and Subscores

Summary statistics, including sample size, mean, median, standard deviation, minimum, maximum, first quartile, third quartile, and 95% CI, will be presented by visits. A mixed-effect model with repeated measurements may be fit for the comparisons between 1.5% BID cream group and vehicle cream group.

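### The SAP leaves a DLQI subscale with a missing answer unscored but has no such rule for CDLQI subscales, where a single blank is scored 0

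*SAP*

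**What the plan says.** SAP 7.2.5.5 scores both instruments on ten questions, each 0 to 3, for a total of 0 to 30. On direction it says: "The higher the score, the more quality of life is impaired".

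**CDLQI.** The item-scoring line includes "Not at all = 0; Question unanswered = 0". Six subscales are then listed. Three imputation rules follow:
- Rule 1 reads: "If 1 question is left unanswered, this is scored 0, and the scores are summed and expressed as usual out of a maximum of 30".
- The next rule reads "2. If 2 or more questions are left unanswered, the questionnaire is not scored".
- Rule 3 takes the higher score when both parts of Question 7 are completed.

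None of the three mentions subscales.

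**DLQI.** The one-blank rule for the total is the same: "If 1 question is left unanswered, this is scored 0 and the scores are summed and expressed as usual out of a maximum of 30". So is the rule for two or more blanks. A further rule has no CDLQI counterpart: "For DLQI 6 subscales, if the answer to 1 question in a subscale is missing, that subscale should not be scored".

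**Use.** SAP 7.5.1.1 plans by-visit summaries of actual values, change and percentage change for "DLQI (or CDLQI) Total score and Subscores", with an optional mixed model. SAP 10.1 moves DLQI/CDLQI from exploratory to secondary, and Appendix A gives the CDLQI its own table (2.9.3). Protocol 8.2.6.5 lists the subscales but no missing-answer rule; it refers to the Study Manual for details.

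**The concern.** The SAP accepts a zero-filled item in a DLQI total but not in a DLQI subscale. That is sensible: one zero among ten items dilutes a total slightly, whereas in a subscale of one to three items it can be most or all of the score. For the CDLQI the zero is defined at item level, the subscales are built from those items, and no exception is stated. A programmer following the text would carry the zero into the subscale.

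Because 0 is the best score, an unanswered question becomes a favourable observation. After baseline, a blank can look like improvement. At baseline, it hides impairment and can make a later genuine answer look like worsening. Subscores for 12- to 15-year-olds would also be derived differently from those of older participants, with no reason given.

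The rule stands apart from the SAP's other questionnaires too. WHO-5 and VitiQoL use no imputation (7.2.5.6, 7.2.5.8), and TSQM and HADS rescale from the answered items (7.2.5.7, 7.2.5.9). None of these replaces a blank with the best score.

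**Working it through.** **1. Reproduce the stated maximum.** 10 questions × 3 = 30, as the SAP says. The CDLQI subscales use each question once: 6 + 9 + 3 + 6 + 3 + 3 = 30.

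**2. One blank in each CDLQI subscale.** The table shows the case where every answered item is 3 and the blank would also have been 3.

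| CDLQI subscale | Questions | Maximum | Score with blank = 0 | Under the DLQI rule |
|---|---|---|---|---|
| Symptoms and feelings | 1, 2 | 6 | 3 | not scored |
| Leisure | 4, 5, 6 | 9 | 6 | not scored |
| School or holidays | 7 | 3 | 0 | not scored |
| Personal relationships | 3, 8 | 6 | 3 | not scored |
| Sleep | 9 | 3 | 0 | not scored |
| Treatment | 10 | 3 | 0 | not scored |

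The understatement is at most 3 points in any subscale. The result is 0 whatever the other answers only in the three single-item subscales. For Q7 this requires the whole question to be unanswered; one empty part of a two-part question need not make it so.

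**3. Like-for-like contrast.** Treatment is Question 10 alone in both instruments. With Q10 blank and the other nine questions answered:
- DLQI: Treatment is missing.
- CDLQI: Treatment = 0 of 3.

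**4. Change from baseline, single-item subscale.**
- Sleep = 3 at baseline, Q9 blank at Week 24: 0 − 3 = −3, the largest improvement the subscale allows.
- Q9 blank at baseline, Sleep = 2 at Week 24: 2 − 0 = +2, whatever the true baseline was.
- Sleep = 0 at baseline, Q9 blank at Week 24: 0 − 0 = 0, no apparent change.

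**5. Totals.** One blank scored 0 lowers a total by at most 3 of 30 in either instrument, which is less than the 4-point change that SAP 7.2.5.5 calls clinically important. The rule for the total is the same in both, and the proposed fix leaves it alone.

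**6. Effect on an arm mean.** One blank replacing a true 3 shifts the mean of a single-item subscale by 3/n, where n is the number of CDLQI completers in that arm. The documents give only a floor for ages 12 to under 18: 10% of about 300 = 30. They give no count for ages 12 to 15 and no rate of blank answers. As an illustration only, assume 10 to 20 CDLQI completers split 2:1. The vehicle arm then has about 3 to 7, and the shift is 3/7 = 0.43 to 3/3 = 1.0 on the 0–3 scale. The active arm has about 7 to 13, and the shift is 3/13 = 0.23 to 3/7 = 0.43. These are worst cases: they need a true answer of 3, a blank on exactly that question, and these assumed numbers.

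**The case against.** The strongest reply is that the SAP never says a blank counts as 0 in a CDLQI subscale. The sentence after the item-scoring line defines the total, and rule 1 applies the zero to a sum out of 30. On that view the subscales have no rule at all. This stands in part: zero-scoring in subscales follows from the item definition together with the absence of an exception. But the item definition is the only instruction a programmer has, and the DLQI text shows that the authors knew an exception was needed.

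Three stronger readings are tempting, and the documents do not support them.
- *Questionnaires with two or more blanks would still yield subscale scores.* The second imputation rule leaves the questionnaire itself unscored, and the subscales are introduced as an analysis of the questionnaire. The natural reading is that nothing is scored, so the problem is limited to exactly one blank.
- *A blank counts as the best possible quality of life.* It gives the best score for that item, and guarantees the best subscale score only for Q7, Q9 and Q10. It says nothing about overall quality of life.
- *Zero-scoring is peculiar to the younger group.* The DLQI total treats one blank the same way; only the subscales differ.

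The difference might also be deliberate. The SAP cites the instrument's validation paper, which is not available here, and the Study Manual may say more. The SAP itself gives no reason. Finally, both arms follow the same rule and the two instruments are reported in separate tables, so no listed pooled result mixes the two derivations. That limits the harm but does not make the recorded zeros correct.

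**Conclusion.** The point holds as an inconsistency in SAP 7.2.5.5 that, applied as written, gives wrong CDLQI subscale values when exactly one question is blank: 0 of 3 in School or holidays, Sleep or Treatment, and an understatement of up to 3 points in the other three subscales.

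It is minor. It touches only by-visit subscore summaries, and the optional mixed model if fitted, for a secondary endpoint outside the fixed sequence in SAP 3.2. A reader might infer a threat to the trial's main conclusions; there is none, since the CDLQI total, the primary endpoint and the key secondary endpoints do not change. The shift in an arm mean is bounded by 3/n per blank, but n is not in the documents, so the illustrative 0.23 to 1.0 should not be read as an expected bias. The conclusion assumes that the item-level zero is what programmers would apply to subscales.

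**What to change.** Add to the CDLQI imputation rules in SAP 7.2.5.5: *For CDLQI subscales, if any question in the subscale is unanswered, that subscale is not scored.* In the item-scoring line, limit the zero for an unanswered question to the CDLQI total; rules 1 and 2 already confine it there to a single blank. If the difference from the DLQI is intended, say so and give the reason.

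The cost is one sentence and a small change to the derivation program. A few CDLQI subscale values become missing, in a group that may be small, so report the number scored for each subscale at each visit.

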7.2.5.6. WHO-5

The WHO-5 is a validated, self-administered, 5-item questionnaire designed to assess mental well-being over the past 2 weeks, which can be used as an outcome measure for the wanted and unwanted effects of treatments ([WHO Collaborating Center for Mental Health, Topp et al 2015](#)). The questionnaire consists of 5 statements, which respondents rate according to the following scale: 0 = At no time; 1 = Some of the time; 2 = Less than half of the time; 3 = More than half of the time; 4 = Most of the time; 5 = All of the time.

The raw score is calculated by totaling the figures of the 5 answers for a range of 0 to 25, with 0 representing the worst possible and 25 representing the best possible quality of life. A score below 13 indicates poor well-being. No imputation will be performed for missing values.

7.2.5.7. Treatment Satisfaction Questionnaire for Medication

TSQM ([Bharmal et al 2009](#)) is a validated 9-item questionnaire that measures a participant's satisfaction with medication taken in a clinical study using a recall period of the past 2 to 3 weeks or since the medication was last used. The TSQM comprises 3 subscales that assess the patient's perception of medication effectiveness, convenience, and global satisfaction. The effectiveness subscale assesses the patient's satisfaction with the ability of the medication to treat the condition and relieve symptoms and the length of time it takes for the medication to start working. The convenience subscale addresses the convenience of administration and ease of planning and following a schedule. The global satisfaction subscale gauges a patient's confidence that the medication is a good thing and that the advantages of taking it outweigh the disadvantages. Each TSQM subscale consists of 3 items, with responses measured on a Likert scale ranging from 1 (low) to 7 (high). Subscale scores were transformed to a range from 0 to 100, with higher scores indicating greater satisfaction.

Scale scoring algorithm ([Atkinson et al 2005](#)) is as follows:

- Effectiveness: $[\text{Item 1} + \text{Item 2} + \text{Item 3} - 3] / 18 \times 100$.
- Convenience: $[\text{Item 4} + \text{Item 5} + \text{Item 6} - 3] / 18 \times 100$.
- If one item in Effectiveness or convenience is missing, the algorithm will be
 $[(\text{Sum of nonmissing items}) - 2] / 12 \times 100$.
- Global satisfaction:
 - First recode Item 9_recode = $(\text{Item 9} - 1) \times 4 / 6 + 1$.
 - Then: $[\text{Item 7} + \text{Item 8} + \text{Item 9_recode} - 3] / 12 \times 100$.
- If 1 item in overall satisfaction is missing, the algorithm will be
 $[(\text{Sum of nonmissing items}) - 2] / 8 \times 100$.

No imputation will be performed for any subscale with missing items ≥ 2 .

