8.2.6.7. Treatment Satisfaction Questionnaire for Medication

TSQM is a validated 9-item questionnaire that measures a participant's satisfaction with medication taken in a clinical study using a recall period of the past 2 to 3 weeks or since the medication was last used. The questionnaire uses a 7-point scale for each question ([Bharmal et al 2009](#)). Full details will be provided in the Study Manual.

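### The TSQM global satisfaction formulas do not fit the 1-to-7 item range stated beside them, and the one-missing-item rule does not say whether the recoded Item 9 is used

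*SAP*

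**What the plan says.** SAP 7.2.5.7 describes a 9-item questionnaire with three subscales: effectiveness (Items 1–3), convenience (Items 4–6) and global satisfaction (Items 7–9). On the items it says: "Each TSQM subscale consists of 3 items, with responses measured on a Likert scale ranging from 1 (low) to 7 (high". On the scores it says: "Subscale scores were transformed to a range from 0 to 100, with higher scores indicating greater satisfaction". Protocol 8.2.6.7 agrees about the items: "The questionnaire uses a 7-point scale for each question". No other section of either document gives a different range for any item.

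The scoring rules in SAP 7.2.5.7 are:

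- **Effectiveness and convenience:** sum of three items minus 3, divided by 18, times 100. With one item missing: sum of the two answered items minus 2, divided by 12, times 100.
- **Global satisfaction:** first recode Item 9 as (Item 9 − 1) × 4/6 + 1. Then add Item 7, Item 8 and the recoded Item 9, subtract 3, divide by 12 and multiply by 100.
- **Global satisfaction, one item missing:** "If 1 item in overall satisfaction is missing, the algorithm will be" the sum of the answered items minus 2, divided by 8, times 100. The SAP says overall here; I take this to be the global satisfaction subscale. The rule does not mention the recoded Item 9.

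TSQM is exploratory (SAP Table 1). It is summarised by treatment and visit (SAP 7.6.1), in Table 2.9.5 and Figure 4.13.1 of Appendix A.

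**The concern.** A score formed as (sum − number of items) / divisor spans 0 to 100 only if the divisor equals the total span of the items. Three items on 1–7 span 18 and two span 12, which are the divisors used for effectiveness and convenience. For global satisfaction the divisors are 12 and 8, which fit three and two items on 1–5. Item 9 is brought to 1–5 by its recode. Items 7 and 8 are not recoded, although the text puts them on 1–7.

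So the section's account of the items and its scoring rule cannot both be right. A programmer must choose, and the choice changes the reported scores. If the item description is right and the formula is applied as printed, global satisfaction sits on a different scale from the other two subscales in the same table, and satisfied participants can score above the stated maximum. The SAP covers both INCB 18424-306 and -307 (SAP 1), so one misreading would enter two study reports.

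**Working it through.** **Inputs.** All come from SAP 7.2.5.7, with the 7-point description also in Protocol 8.2.6.7: items 1 to 7; subscale scores 0 to 100; Item 9 recode (Item 9 − 1) × 4/6 + 1; global satisfaction divisors 12 (complete) and 8 (one missing).

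**Step 1: the subscales that reproduce the stated range.** With all items at 1 the score is 0. With all items at 7:

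- complete: (7 + 7 + 7 − 3)/18 × 100 = 100
- one missing: (7 + 7 − 2)/12 × 100 = 100

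Effectiveness and convenience therefore run exactly 0 to 100.

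**Step 2: the recode.** Item 9 = 1 gives (1 − 1) × 4/6 + 1 = 1. Item 9 = 7 gives (7 − 1) × 4/6 + 1 = 5. The recode maps 1–7 to 1–5.

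**Step 3: global satisfaction.** The documents do not settle two things: whether Items 7 and 8 run 1–7 or 1–5, and whether raw or recoded Item 9 enters the one-missing rule. The minimum is 0 in every case. The maxima are:

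| Case | Items 7 and 8 on 1–7 (as stated) | Items 7 and 8 on 1–5 (implied by divisors) |
|---|---|---|
| Complete | (7 + 7 + 5 − 3)/12 × 100 = 133.3 | (5 + 5 + 5 − 3)/12 × 100 = 100 |
| Item 9 missing | (7 + 7 − 2)/8 × 100 = 150 | (5 + 5 − 2)/8 × 100 = 100 |
| Item 7 or 8 missing, raw Item 9 | (7 + 7 − 2)/8 × 100 = 150 | (5 + 7 − 2)/8 × 100 = 125 |
| Item 7 or 8 missing, recoded Item 9 | (7 + 5 − 2)/8 × 100 = 125 | (5 + 5 − 2)/8 × 100 = 100 |

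With items on 1–7 and none missing, enumerating all 7 × 7 × 7 = 343 response patterns puts 33 of them above 100. This is a count of possible patterns, not a forecast of how many participants would be affected.

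**Step 4: size of the raw-versus-recoded difference.** For a given answer to Item 9, raw minus recoded is (Item 9 − 1) − (Item 9 − 1) × 4/6 = (Item 9 − 1)/3. Divided by 8 and multiplied by 100, that is 0 points at Item 9 = 1 and (6/3)/8 × 100 = 25 points at Item 9 = 7. It arises only when Item 7 or Item 8 is the missing item, and it grows with satisfaction.

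**Step 5: do the repairs work?**

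- Items 7 and 8 stated as 1–5, with recoded Item 9 in both rules: maximum 100 in every case (right-hand column, omitting the raw row).
- All items kept at 1–7, raw Item 9, divisors 18 and 12: the same formulas as Step 1, maximum 100.
- All items at 1–7, with Items 7, 8 and 9 all recoded to 1–5 and divisors 12 and 8: (5 + 5 + 5 − 3)/12 × 100 = 100 and (5 + 5 − 2)/8 × 100 = 100.

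**The case against.** The strongest reply is that the scoring is probably right and one descriptive sentence is loose. Three parts of the algorithm agree: Item 9 alone is recoded to 1–5, the complete divisor is 12, and the one-missing divisor is 8. All three make sense if Items 7 and 8 are 1–5 items. A program written to the algorithm would then give correct complete-item scores, and 133 and 150 would never occur. This is plausible. But the documents do not confirm it: both put these items on 1–7, and neither shows the response options.

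A second reply concerns the one-missing rule. It follows directly after the instruction to recode Item 9, and its divisor of 8 fits only 1–5 items, so carrying the recode over is the natural reading. That too is fair. The rule is silent on the recode; it does not reject it.

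For these reasons the documents do not support a stronger reading that a reader might infer, namely that the 0–100 range is broken whichever item range is true. If Items 7 and 8 run 1–5 and the recode carries over, every formula gives exactly 0 to 100. On 1–5 items the fault is an ambiguity, and it produces scores above 100 only if raw Item 9 is used.

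Finally, the stakes are low. The endpoint is exploratory and descriptive, both arms are scored by the same rule, and no cross-subscale analysis is planned. That limits the importance of the point but does not remove the contradiction.

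**Conclusion.** SAP 7.2.5.7 is wrong as written: its item range and its global satisfaction formulas cannot both hold with a 0–100 score. On the stated 1–7 range, the maximum is 133 with complete items and 125 to 150 with one missing, depending on which item is missing and how Item 9 enters. On a 1–5 range for Items 7 and 8, complete scores are correct, and what remains is an unspecified treatment of Item 9 worth up to 25 points for participants missing Item 7 or Item 8.

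The inconsistency itself rests on no assumption beyond the printed text. Its consequence depends on the true response options, which the documents do not give. A reader might infer that reported TSQM results will be wrong, or that the trial's main conclusions are touched. Neither follows: the program may apply the intended range, and no primary or key secondary test uses TSQM. Effectiveness and convenience are scored correctly. The point is minor.

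**What to change.** Check the response options for Items 7, 8 and 9 in the eCRF, the scoring instructions in the Study Manual, and the source that SAP 7.2.5.7 cites for the algorithm. Then:

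- **If Items 7 and 8 are 1–5:** correct the item-range sentence in SAP 7.2.5.7 and the 7-point statement in Protocol 8.2.6.7. Keep the divisors.
- **If Items 7 and 8 are 1–7:** either recode them with the Item 9 formula and keep divisors 12 and 8, or use raw items throughout with divisors 18 and 12.
- **In either case:** make the one-missing rule explicit, by naming the recoded Item 9 wherever the 12 and 8 divisors are kept, or by stating the matching divisor. Use one name for the subscale.
- **Programming:** add a check that every derived subscale score lies between 0 and 100.

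The cost is a few words in the SAP, possibly one sentence in the protocol, and one programming check. Sites have nothing to change.
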